12.0 Statistical Data Management

Research materials that will be directly obtained from the participants are: (1) questionnaires; (2) standard measures of height, weight, and waist circumference; (3) blood samples; and (4) urine specimens to determine pregnancy status (women only). Only members of the research team directly involved in the proposed trial will have access to individually identifiable private information about the participants. All research material collected during the proposed project will be used for research purposes only and will be kept strictly confidential. The only research materials that will be obtained from other sources are the recruitment data: potential participants' medical records will be accessed in accordance with HIPAA and IRB regulations when the Eskenazi EMR is searched to generate a list of patients who satisfy the study inclusion/exclusion criteria.

REDCap software will be used to obtain the questionnaire data and other data (e.g., height, weight, waist circumference, and urine pregnancy test results). Blood samples will be transferred from the Indiana CTSI Clinical Research Center (CRC) to Translation Core Analyte Lab of the Indiana CTSI for secure storage until the time of assay. An Excel file reporting assay results will be securely sent to [name] from the Translation Core Analyte Lab. SPSS statistical software will be used for all data merging, cleaning, and reduction tasks.

13.0 Privacy/Confidentiality Issues

Participants will be screened in the privacy of their homes via phone or the Indiana CTSI Clinical Research Center (CRC). All procedures will take place in private rooms at the CRC, [name] Behavioral Medicine Laboratory, the targeted primary care clinics, or a location selected by the patient, such as their home or a family member's/friend's home (for calls and the computerized and telephonic components of the treatment groups). All

research material will be kept strictly confidential. All study personnel have completed the required Collaborative Institutional Training Initiative (CITI) courses and will make every effort to ensure confidentiality. All electronic and hard copy data will be identified using only the unique participant number assigned when each individual is enrolled in this study (participant identifying information will not be included). All electronic data will be saved on password-protected and encrypted computers and secure servers, and all hard copy data will be stored in secure and locked file cabinets. The key linking participant names with the participant numbers will be kept in a separate secure and locked file cabinet. Data will be analyzed and reported as an aggregate, with no individual identifying information. Any leftover blood samples will be stored in [name] laboratory.

14.0 Follow-up and Record Retention

Participants in both treatment groups who continue to exhibit elevated depressive symptoms (PHQ-9 ≥ 10) at post-treatment will be urged to follow-up with their primary care providers regarding their depression. Their providers will also receive a letter from the study team indicating that their patient has completed participation in the treatment phase of the trial and continues to have elevated depressive symptoms. This letter will also urge physicians to follow-up with their patients and will provide a list of local mental health services.

While the study duration (i.e., project period) is 2 years, all study documents will be kept up to 7 years after study completion. After this time, we will permanently delete patient identifying data and shred all paper records, per Indiana State law. This process prevents any opportunity for a breach of confidentiality to occur.

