Treatment Process. At the end of the pre-treatment visit, our DCS will speak to the patient for 20 minutes via IU Zoom Health to orient them to depression materials and schedule the intake interview. Future DCS contacts will be over the phone or via IU Health Zoom, consistent with patient preference. Our DCS will contact the patient for the intake interview. At meetings every 2 weeks, the DCS will present cases to our team, who will formulate a Step 1 plan with PCP input. The DCS will work with the PCP to implement this plan. Step 1 will be 2 months of psychotherapy or an antidepressant. GDA and PST-PC are our first- and second-line psychotherapies; bupropion and fluoxetine are our first- and second-line antidepressants (others are third-line). For patients on an antidepressant at entry, the dosage may be increased, psychotherapy may be added, or a different antidepressant may be prescribed. For patients who want psychotherapy but have major barriers to GDA, PST-PC will be offered at Step 1. Our DCS will follow patients for 6 months, while monitoring response and staffing cases with the team at least every 2 months. At the start, the DCS will have sessions at least every 2 weeks. For patients who achieve remission ($\geq 50\%$ PHQ-9 reduction and < 3 symptoms⁵⁰), the DCS will develop a relapse prevention plan and follow-up monthly. Step 2 – augmenting Step 1 with psychotherapy or an antidepressant or switching to another psychotherapy or antidepressant – will be delivered to patients not in remission. If remission is not achieved after Step 2, Step 3 will be initiated, which will involve additional psychotherapy and/or antidepressants.

PHQ-9 Score	Action (within 24 hours)
<10 (minimal)	Results will be reported in a note added to the EMR.
10-19 (minor/moderate)	RA will encourage patient to seek treatment at their primary care clinic and will notify the patient's PCP and the embedded behavioral health clinician.
20-27 (severe)	RA will strongly encourage patient to seek treatment at their primary care clinic and will notify the patient's PCP, the embedded behavioral health clinician, and the affiliated psychiatrist.

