Active Control (AC) consists of depression education (study staff), symptom monitoring (study staff), and primary care for depression (clinical staff). (1) At the end of the pre-treatment visit, the RA responsible for Active Control delivery (a clinical psychology PhD mentee of the PI) will speak to the patient for 20 minutes via IU Zoom Health to review depression materials,¹¹⁵ including their PCP's role in its management and treatment options. In addition, patients will be provided with a list of Eskenazi

mental health services, and the RA will encourage patients to follow-up with their PCP. To engender expectancy of benefit, the RA will stress that our notifications should prompt PCP actions and that the available treatments are effective. We will then send an EMR message to the PCP indicating that their patient has a depressive disorder and was randomized to the AC group. This message will encourage the PCP to address their patient's depression, note that there are no care restrictions, and provide the same list of Eskenazi services. (2) The RA will call AC patients every 4 weeks (i.e., at the end of Months 1, 2, 3, 4, and 5) to assess depressive symptoms (PHQ-9) and will notify clinical staff to encourage additional care when indicated (see table). (3) AC patients will receive current primary care for depression. The Eskenazi primary care clinics utilize a team care approach for behavioral health issues, as PCPs are supported by embedded behavioral health clinicians and affiliated psychiatrists available for brief counseling and antidepressant management.

We chose an AC comparator¹¹⁶ for several reasons. (1) Because we plan to use an AC group in the R01-level RCT, we need to use it here to obtain accurate effect size estimates. Other approaches (no comparator or usual care comparator) could overestimate effect sizes. (2) Our AC group will help to ensure that the groups have similar expectancy of benefit and clinical

attention. We will assess expectancy⁸³ and attention and will adjust for them in a sensitivity analysis. (3) Our AC group is feasible. As eIMPACT-DM uses a flexible approach, each patient will have their own treatment path within the intervention structure. Thus, it is not possible to develop a comparator that exactly parallels the attention for each eIMPACT-DM patient.

Type	Name	Description

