Suicidal ideation will be assessed using Item #9 of the PHQ-9 at the pre- and post-treatment visits. The PHQ-9 may also be administered periodically in person by the depression clinical specialist during the treatment phase. Suicidal ideation will also be assessed using items #3 "thoughts of ending your life" and #14 "thoughts of death or dying" on the SCL-20 at pre- and post-treatment visits.

If an enrolled patient reports having thoughts of being better off dead or of hurting him/herself (i.e., responds with a 1, 2, or 3 to PHQ-9 Item #9; responds with a 1, 2, 3, or 4 to SCL-20 Item #3 or #14; or spontaneously reports suicidal ideation) during an in-person study visit, the visit will be immediately stopped, and the research assistant or depression clinical specialist will interview the participant to complete the Patient Suicidality Form. If the potential participant answers "no" to the clarifying question, the visit will proceed as normal. If the

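### A post-treatment PHQ-9 of 20–27 without a positive suicidality form brings only advice and an undated provider letter, although Active Control calls at Months 1–5 send a 24-hour notice to three clinicians at that score

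*Combined protocol and SAP*

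**What the plan says.** Section 14.0 (Follow-up and Record Retention) sets the post-treatment rule for both arms. Patients scoring 10 or more on the PHQ-9 "will be urged to follow-up with their primary care providers regarding their depression". For the provider, "Their providers will also receive a letter from the study team indicating that their patient has completed participation in the treatment phase" and that depressive symptoms remain elevated; the letter also encourages follow-up and encloses a list of services. The section gives no time limit, does not separate 20–27 from 10–19, and names no recipient beyond the patient's providers.

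Section 7.0 (Study Procedures) holds a graded PHQ-9 table whose second column is headed "Action (within 24 hours"). At 10–19 the PCP and the embedded behavioral health clinician are told. At 20–27 the notice goes to the PCP, "the embedded behavioral health clinician, and the affiliated psychiatrist". The table belongs to the Active Control arm: "The RA will call AC patients every 4 weeks (i.e., at the end of Months 1, 2, 3, 4, and 5"), and the research assistant (RA) "will notify clinical staff to encourage additional care when indicated (see table"). For the intervention arm, the depression clinical specialist follows patients for 6 months "while monitoring response and staffing cases with the team at least every 2 months".

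Section 16.0 (the Suicidal Ideation Protection Protocol) also runs at the post-treatment visit. It is opened by PHQ-9 item 9, SCL-20 item 3 or 14, or a spontaneous report, not by the total score. A positive form brings same-day review and PCP notice. After a negative answer "to the clarifying question, the visit will proceed as normal".

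**The concern.** The post-treatment visit is the last planned study contact about depression care. It comes at Month 6, about 4 weeks after an Active Control call at the end of Month 5. If the five calls run strictly every 4 weeks, the last is at week 20 and the gap to week 26 is 6 weeks. A patient can leave this visit with a score in the trial's own severe band while the protocol sets no time by which any clinician must learn of it. The same score at the Month 5 call would reach three clinicians within a day.

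What is at stake is patient safety for a small number of people. The primary and secondary outcomes come from blood drawn at the same visit and cannot be influenced.

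**Working it through.** The plan gives no figure to reproduce here. The check is a comparison of the text, followed by an illustrative count.

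**1. Response to a score of 20–27, by occasion**

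| Occasion | Arm | Time limit | Clinicians told |
|---|---|---|---|
| Monitoring calls, Months 1–5 (7.0) | Active Control | 24 hours | PCP, behavioral health clinician, psychiatrist |
| Post-treatment, positive suicidality form (16.0) | Both | Same-day review | Study psychologist and psychiatrist review; PCP notified |
| Post-treatment, no positive form (14.0) | Both | None stated | Provider, by letter |

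**2. How a severe score can miss the suicidality route**
- The form is never opened. With item 9 at 0, the other eight items can total 8 × 3 = 24, so 20–24 is possible if both SCL-20 items are 0 and nothing is volunteered.
- The form is opened and closed by a negative answer to the clarifying question.
- The form is closed by negative answers to all three suicide questions, or by a past attempt at least 10 years ago as the only positive answer. It then goes to the principal investigator, and no provider notice is stated.

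**3. How many patients score 20–27**

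Inputs: post-treatment PHQ-9 mean (SD) in the eIMPACT Trial, Section 1.0 (C2): 8.0 (6.4) intervention and 11.9 (5.8) usual care, at 12 months. Completers: 25 per arm, Section 11.0. Usual care stands in for Active Control.

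Normal model: P(score ≥ 20) = 1 − Φ((20 − mean)/SD), with 19.5 in place of 20 for the continuity correction.
- Intervention: (20 − 8.0)/6.4 = 1.875, P = 0.030; corrected 0.036. Times 25: 0.8 to 0.9.
- Control: (20 − 11.9)/5.8 = 1.397, P = 0.081; corrected 0.095. Times 25: 2.0 to 2.4.
- Total: 2.8 to 3.3 of 50.

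Models bounded to 0–27:
- Beta-binomial: 0.064 and 0.112, or 1.6 + 2.8 = 4.4.
- Truncated normal: 0.066 and 0.105, or 4.3.

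The range is 2.8 to 4.4, so about 3–4 of 50. Positive forms should then be removed, but the documents give no rate. At an assumed 0–50%, 1.4 (2.8 × 0.5) to 4.4 remain.

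**4. What Active Control providers would already know**

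Assume the same N(11.9, 5.8) margin at every month and a Month 5–6 correlation of 0.5 to 0.9. Among Active Control patients with a Month 6 score of at least 20:
- 92–100% scored at least 10 at Month 5, so their PCP and behavioral health clinician had already been notified.
- 30–69% scored at least 20 at Month 5, so the psychiatrist had been notified too.
- 49–80% (correlation decaying with time) or 68–91% (equal correlation) scored at least 20 at one or more of the five calls.

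So 9–51% of the 2.0 to 2.8 Active Control patients severe at Month 6 had no earlier psychiatrist notice: 2.0 × 0.09 = 0.2 to 2.8 × 0.51 = 1.4 patients.

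**The case against.** The best case for the plan is that no rule is broken and little is lost. The graded table is an Active Control component that prompts care during treatment, and treating it as the standard for an end-of-trial handover is a choice. Suicidality, the most urgent risk, has its own same-day route. Providers are not in the dark: Active Control PCPs are told of the depressive disorder at entry and again after each monthly score of 10 or more, while intervention patients have had six months of care involving a psychiatrist and the PCP. Section 8.0 also mentions safety protocols and manuals that are not in this document and may hold operating detail.

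Most of this stands and limits the size of the point. It does not supply a time limit for the Month 6 score, and earlier contacts do not convey that score.

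A reader might infer more than the text supports:
- **That Section 14.0 contradicts the 24-hour table.** It does not; that table covers the Active Control calls only.
- **That severely depressed patients leave the trial without any clinician knowing.** Step 4 of the working and the collaborative care model argue against this.
- **That every score of 10 or more needs the 24-hour notice.** About 25–27 of 50 completers would score that high (normal model: 0.377 to 0.407 and 0.628 to 0.660, each times 25). The severe-score gap does not require notices for all of them.

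**Conclusion.** The point holds as a modest patient-safety improvement. As written, a post-treatment score of 20–27 without a positive suicidality form gets no faster or wider notice than a score of 10, in either arm, although the trial already runs a 24-hour route for the same score elsewhere. That much rests on the text alone.

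The size is illustrative: about 3–4 of 50 completers, fewer once positive forms are removed. It depends on interim 12-month scores from a trial with a different computerized therapy, on usual care standing in for Active Control, on 25 completers per arm, and on assumed correlations between months. For most of these patients the gain is prompt delivery of the Month 6 score. A psychiatrist notice would be new only for those not already severe at an earlier call, and intervention patients already have psychiatrist involvement. Staff may act faster in practice than the document requires. No estimand, power statement or analysis changes.

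**What to change.** Add a sentence or two to Section 14.0. In both arms, for a post-treatment PHQ-9 of 20–27, a designated study staff member who is not a blinded outcomes assessor sends a notice of the score through the medical record within 24 hours. It goes to the PCP, the embedded behavioral health clinician and the affiliated psychiatrist. The notice does not name the arm, and nothing about the arm goes back to the assessor, so the blinding in Section 5.0 is kept. The depression clinical specialist or the RA who delivers Active Control could send it.

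Keep the present advice and letter for scores of 10–19. Extending the 24-hour notice to that tier is optional.

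Cost: about 3–4 extra notices over the whole trial and a one-way handoff of the score from the assessor. The PHQ-9, record messaging and staff are already in place. Care prompted by the notice could touch the exploratory five-year diabetes outcome slightly, but Section 14.0 already encourages that care.

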16.0 Appendix: Suicidal Ideation Protection Protocol

Suicidal ideation protection protocols very similar to the one described below have previously been approved by the Indiana University IRB and were successfully implemented in three other depression trials conducted by our team (IRB #'s 1105005448, 1110007119, and 1411802537). Those suicide management plans were constructed with input from Sandra Eskenazi Mental Health Center leadership ([name], Associate Vice President, and [name]), who concluded that the plans provide a high level of protection while minimizing disruption to usual clinical activities. The informed consent form for this trial contains a section describing the steps that will be taken if an enrolled patient reports suicidal ideation on a questionnaire or spontaneously.

ResNet Phone Screening Interview

If a potential participant reports having thoughts of being better off dead or of hurting him/herself (i.e., responds with a 1, 2, or 3 to PHQ-9 Item #9 or spontaneously reports suicidal ideation) during a ResNet telephone interview, the interview will be immediately stopped, and the ResNet research assistant will interview the potential participant to complete the Patient Suicidality Form. If the potential participant answers "no" to the clarifying question, the interview will proceed as normal. If the potential participant answers "yes" to the clarifying question, the participant will be asked the three suicide questions. If the potential participant answers "no" to all three suicide questions or if the patient answers "yes" only to Question 3 (previous attempt) and the most recent attempt was \geq 10 years ago, the interview will proceed as normal, and the completed Patient Suicidality Form will be given to the principal investigator. If the potential participant answers "yes" to any of the three questions (for Question #3 the previous attempt must be within the past 10 years), the ResNet research assistant will inform the patient that the interview must be stopped and that a behavioral health clinician must be contacted according to the study protocol. The patient will also be told that the behavioral health clinician will call them back before the end of that day. The ResNet research assistant will then contact a behavioral health clinician, who will contact the patient before the end of that day to determine the appropriate course of action (e.g., referral to the psychiatrist or to the Crisis Intervention Unit) and will notify the patient's primary care provider. After the situation is handled, the ResNet research assistant will contact the behavioral health clinician. If the behavioral health clinician considers the patient to be at acute risk of suicide (an exclusion criterion), the patient will be coded as ineligible. If the behavioral health clinician considers the patient *not* to be at acute risk of suicide, ResNet will attempt to contact the patient again to readminister the screening interview.

In-Person Study Visits

Suicidal ideation will be assessed using Item #9 of the PHQ-9 at the pre- and post-treatment visits. The PHQ-9 may also be administered periodically in person by the depression clinical specialist during the treatment phase. Suicidal ideation will also be assessed using items #3 "thoughts of ending your life" and #14 "thoughts of death or dying" on the SCL-20 at pre- and post-treatment visits.

If an enrolled patient reports having thoughts of being better off dead or of hurting him/herself (i.e., responds with a 1, 2, or 3 to PHQ-9 Item #9; responds with a 1, 2, 3, or 4 to SCL-20 Item #3 or #14; or spontaneously reports suicidal ideation) during an in-person study visit, the visit will be immediately stopped, and the research assistant or depression clinical specialist will interview the participant to complete the Patient Suicidality Form. If the potential participant answers "no" to the clarifying question, the visit will proceed as normal. If the

potential participant answers “yes” to the clarifying question, the participant will be asked the three suicide questions. If the participant answers “no” to all three suicide questions or if the patient answers “yes” only to Question 3 (previous attempt) and the most recent attempt was \geq 10 years ago, the visit will proceed as normal, and the completed Patient Suicidality Form will be given to the principal investigator. If the participant answers “yes” to any of the three questions (for Question #3 the previous attempt must be within the past 10 years), the research assistant or depression clinical specialist will immediately contact [name]. If [name] cannot be reached, contact [name]. [name] (a clinical psychologist) and [name] (the trial psychiatrist) will review the case as soon as possible, but no later than the same day, to determine the appropriate course of action (e.g., interview the patient to obtain further information, immediately contact the patient’s primary care provider and/or behavioral health clinician to involve them in the decision-making process, consult with clinicians at Sandra Eskenazi Mental Health Center, escort the patient to the Crisis Intervention Unit, and/or contact the police if the patient is at imminent danger of harm and is refusing all care). The depression clinical specialist will also notify the participant’s primary care provider if s/he was not involved in the decision-making process. Regardless of the exact course of action, the study team will ensure that the participant is connected to the appropriate existing clinical services. If the patient’s primary care provider no longer believes that the patient is appropriate for this trial following a situation, s/he will be withdrawn.

Study Calls

Suicidal ideation will be assessed using Item #9 of the PHQ-9 during most study calls completed by the depression clinical specialist responsible for intervention delivery and during most study calls completed by the research assistant responsible for active control delivery.

If an enrolled patient reports having thoughts of being better off dead or of hurting him/herself (i.e., responds with a 1, 2, or 3 to PHQ-9 Item #9 or spontaneously reports suicidal ideation) during a study calls, the research assistant or depression clinical specialist will immediately interview the participant to complete the Patient Suicidality Form. If the potential participant answers “no” to the clarifying question, the call will proceed as normal. If the potential participant answers “yes” to the clarifying question, the participant will be asked the three suicide questions. If the participant answers “no” to all three suicide questions or if the participant answers “yes” only to Question 3 (previous attempt) and the most recent attempt was >10 years ago, the call will proceed as normal, and the completed Patient Suicidality Form will be given to the principal investigator. If the participant answers “yes” to any of the three questions (for Question #3 the previous attempt must be within the past 10 years) or prematurely terminates the call, the research assistant or depression clinical specialist will immediately contact [name]. If [name] cannot be reached, contact [name]. Drs. [name] and [name] will review the case as soon as possible, but no later than the same day, to determine the appropriate course of action (e.g., interview the patient to obtain further information, immediately contact the patient’s primary care provider and/or behavioral health clinician to involve them in the decision-making process, consult with clinicians at Sandra Eskenazi Mental Health Center, refer the patient to the Crisis Intervention Unit, and/or contact the police if the patient is at imminent danger of harm and is refusing all care). The depression clinical specialist will also notify the participant’s primary care provider if s/he was not involved in the decision-making process. Regardless of the exact course of action, the study team will ensure that the participant is connected to the appropriate existing clinical services. If the patient’s primary care provider no longer believes that the patient is appropriate for this trial following a situation, s/he will be withdrawn.

Patient Suicidality Form

Interviewer: _____ Date: _____

Patient's Name: _____ Hospital ID: _____

Patient's Address: _____

Patient's Phone Number: _____ Patient's PCP: _____

Clarifying Question***Over the past 2 weeks, have you been having thoughts of hurting yourself in some way?***Yes _____ No _____
(Continue) (Stop, no SIPP trigger)

Comments:

I'm going to ask you a few questions that are part of the study protocol, because we have seen that in some patients with these symptoms, these are important concerns.***1. Do you have a suicide plan?***

Yes _____ No _____

Comments:

2. Have you been struggling against thoughts about committing suicide? In other words, are you afraid you might act on these thoughts?

Yes _____ No _____

Comments:

3. Have you attempted suicide in the past?

Yes _____ No _____

If YES, in what year was the most recent attempt? _____

Comments:

If the patient answers "yes" to any of the three questions (for Question #3 the previous attempt must be within the past 10 years), you must carefully follow the procedures described in the Suicidal Ideation Protection Protocol.
